3 STUDY DESIGN

[figure not shown]
3.1 General study design

This multicenter Phase 3 study is comprised of two parts. The first part of the study is a randomized, double blind, placebo-controlled, phase which aims to demonstrate efficacy and safety of BoNT/A-DP compared with placebo. The second part is an open label extension phase to evaluate efficacy after repeat treatments and long term safety.

Subjects can receive a maximum of four treatment cycles over the duration of the study, a single treatment in the first cycle compared with placebo, and up to three subsequent treatments in the open label extension study.

Adult subjects less or equal 75 years old with moderate to severe glabellar frown lines at maximum frown with an important psychological impact as indicated by scores >0 on either the Emotional or Functioning subscales of the modified Skindex-16 (GL-QoL) will be enrolled in this study. Approximately 18 sites (50% in EU and 50% in US) will enroll in total 700 evaluable subjects. Applying a 10% drop out rate will result in a total number of completing subjects of about 630.

The overall study scheme is presented below:

[figure not shown]

The duration of study participation for each subject will be up to 14 calendar days of screening followed by 48 to 60 weeks of treatment (re-screening will not be permitted). The first treatment cycle will be a double blinded cycle followed by up to three open label treatment cycles. Each cycle will be at least 12 weeks and can be prolonged in 4-week increments, depending on treatment effect. Re-treatment is possible until study-week 48.

[figure not shown]
Statistical Analysis Plan (SAP)

Visit Scheme/Treatment Cycle 1 (double blind)

Visit Scheme/Treatment Cycles 2, 3, 4 (open label)

Statistical Analysis Plan (SAP)

3.2 Randomization and blinding

3.2.1 Randomization

This is a randomized, double blind, placebo-controlled efficacy and safety clinical study followed by an open label extension. Subjects will be randomly assigned to receive either BoNT/A-DP or placebo at a ratio of 3:1 respectively in the first treatment cycle. The 3:1 ratio in favor of active treatment versus placebo has been selected to increase the safety data base size.

Randomization will be performed per study site via interactive web response system (IWRS). One unique randomization code will be assigned to each subject.

3.2.2 Blinding

For the first placebo controlled treatment cycle (the double-blind cycle of this trial), BoNT/A-DP and placebo will be provided to the sites in glass vials. Since BoNT/A-DP-vials contain a pellet of lyophilized BoNT/A-DP, they can be discerned from placebo-vials (empty vials). However, after reconstitution by an unblinded study team member at the site, both will look identical (clear solution, comparable volume), thus maintaining the blind. The unblinded study team member preparing the Investigational Medicinal Product (IMP) at the study site must not, by any means, be involved in any other study data collection activities including Adverse event (AE) assessment, case report form (CRF) completion, diary collection etc. IMP will be assigned to the subjects by IWRS with the lot number and kit number assigned corresponding to the group to which the subjects are assigned (blinded medication number and batch/lot number during the double-blind phase of the study at the given site). Once a subject has entered the open label extension, this unblinded study team member can then be involved in data collection activities with regard to that particular subject. The assigned vial will be reconstituted and will be forwarded to the investigator for injection. Specific Blinding Plans will be created at each study site during the Study Initiation visits, defining the Unblinded Study Team and the process of maintaining the blind by this Unblinded Study Team towards the blinded rest of the team.

3.2.3 Unblinding

The decision to unblind lies fully with the investigator. The randomization assignment should not be revealed before the study has been completed and the database has been cleaned and closed. The study will be unblinded using the Study Specific Unblinding Procedure (an unblinding module is standard on all blinded studies; also it is possible to grant access to regulatory unblinding users so that they can monitor the safety of the study, if required).

Statistical Analysis Plan (SAP)

In case of emergency, the IMP administered to the subjects can be revealed using the unblinding function of the IWRS.

In rare emergencies, unblinding may be necessary for the clinical management of an AE. Investigators should consider unblinding only if knowledge of the administered product will have an influence on the further treatment of the AE. In such events, the investigator should make every attempt to inform the Sponsor before breaking the blind or as soon as possible after unblinding has been performed. The [REDACTED] or CROMA medical team is available to discuss any unblinding need. However, such discussion is not mandatory. The investigator can always unblind as per his/her discretion if the actual treatment information is considered relevant for subsequent event treatment. Once unblinding has occurred, the site should immediately contact the [REDACTED] or CROMA medical team. Communication of the unblinding result is considered acceptable. It is at the discretion of the investigator to continue an unblinded subject in the study. The date and time of breaking the code, the reason for breaking the code, study product administered, subject identification number and randomization code will be documented within the IWRS.

3.3 Study treatments and assessments

Subjects will participate in this study for a duration of 50 to 62 weeks from signing the informed consent form (ICF) to the End of Study visit (i.e. up to 14 calendar days for screening, followed by 48 to 60 weeks study participation).

The first treatment cycle of the study will comprise two treatment groups as follows:

- Group A (active): BoNT/A-DP (20 units, 0.5 mL).
- Group B (placebo control): sterile, 0.9% sodium chloride (0.5 mL).

Eligible subjects will be randomized at baseline (day 0) to Group A or B to receive the first treatment in a 3:1 randomization scheme, respectively. Investigators and subjects will be blinded to the treatment administered and will evaluate the severity of glabellar lines independently. The subjects must perform their assessment independently and ideally before the investigator, to ensure they are not biased by the investigator. The same investigator must assess the subject at baseline and at the visits at weeks 1, 2 and 4 in the first treatment cycle.

After a screening period of up to 14 calendar days, subjects will receive the first treatment (BoNT/A-DP or placebo) and attend for visits at 1, 2 and 4 weeks after treatment and at 4-weekly intervals thereafter for evaluation of efficacy and safety (primary and key secondary efficacy endpoints will only be evaluated in the first treatment cycle in comparison with placebo). Re-screening will not be permitted.

Statistical Analysis Plan (SAP)

The effect of botulinum toxin typically lasts a few months, hence the first treatment cycle will last at least 12 weeks and will end when the subjects qualify for re-treatment.

After the first treatment cycle is completed, all subjects may enter the open label extension phase and will be dosed with BoNT/A-DP (20 U) for subsequent re-treatments.

Subjects will attend for visits at one and four weeks after re-treatment and at 4-weekly intervals thereafter. Additional telephone call follow-ups will take place in the open label extension phase two and eight weeks after each re-treatment. Each re-treatment cycle will last at least 12 weeks and will end when the subject qualifies for re-treatment or with the End of Study visit. According to the study schedule, a maximum of four treatments per subject (four treatment cycles) is permitted during the study time frame, with treatments separated by a minimum of 12 weeks.

A subject may move to the next treatment cycle if more than 12 weeks have passed since the previous treatment. Starting at week 12 and at 4-weekly intervals thereafter, subjects will attend the site for the Evaluation for Re-treatment visit. If the subject has a Facial Wrinkle Scale (FWS) score (at maximum frown) of ≥ 2 , as determined by both the subject using the Glabellar Line Scale for Subjects (GLS-S) and the investigator using the Glabellar Line Scale for Investigators (GLS-I), this visit on the same day at the same site visit will then be considered the End of Cycle visit and all other criteria required to determine eligibility for re-injection will be assessed e.g. negative urine pregnancy test (in women of child-bearing potential), lack of infection or inflammation in the planned injection area etc. Furthermore, all additional tests e.g. laboratory tests required for final cycle assessment will be performed. If the subject qualifies for re-treatment, on the same day at the same site visit, the subject will then enter the next treatment cycle and will receive the next study drug treatment as part of the Re-Treatment visit (i.e. day 0 of the next treatment cycle).

If the FWS score (at maximum frown) is assessed as ≥ 2 by both the investigator and the subject, but the additional criteria for reinjection are not met, e.g. relevant infection or inflammation at the injection site, the subject may attend for a visit 4 weeks thereafter. Subjects with a positive pregnancy test, or subjects who do not agree to re-treatment, will be withdrawn from the study and the End of Study visit will be conducted at the earliest opportunity.

If at an Evaluation for Re-treatment visit the subject wants to get re-treated, but the investigator does not agree or vice versa (i.e. the FWS score is not \geq at least 2 by both assessments), the subject will return to the site four weeks thereafter for another Evaluation for Re-treatment visit. There is no limit to the number of Evaluation for Re-treatment

Statistical Analysis Plan (SAP)

visits. In order to consider a visit as the End of Cycle visit, there must always be agreement between investigator and subject on a FWS score (at maximum frown) of ≥ 2 .

The End of Study visit can take place in four-weekly intervals from study-week 48 until study-week 60. The last study drug re-treatment will be administered no later than week 48. For subjects receiving a re-treatment at week 48, the last cycle will end 12 weeks later at week 60 (i.e. End of Study visit).

The End of Study visit will take place at week 48 if the week 48 visit is an Evaluation for Re-treatment visit and the subject does not meet the criteria for re-treatment in case this visit is 12 or more weeks after the last treatment. As week 48 is the last possible time point for re-treatment, such subjects will continue with all additional assessments of the End of Study visit on the same day. For subjects having received their last injection eight weeks or less prior to week 48, the End of Study visit will take place 12 weeks after the last study drug treatment was given, e.g. week 52 if the subject was re-treated at week 40.

For subjects who are prematurely discontinued from the study (at any time), the End of Study visit will take place within one week of discontinuation.

A detailed description of procedures and assessments to be conducted during this study is summarized in the Scheduled of Study Assessments in Table 1 below.

Statistical Analysis Plan (SAP)

Table 1: Schedule of Study Assessments

Procedures and assessments	Double-blind phase								Open label phase							
	Cycle 1 (C1)				Cycle 2 (C2) ¹				Cycle 3 (C3) ¹				Cycle 4 (C4) ¹			
	1	2	3	4	5	6	7	8	9	10	11	12	13	14	15	16
Visit No*/**																
Informed consent	x															
Consent for re-treatment																
Eligibility: Inclusion/Exclusion	x	x														
Eligibility for re-treatment					x											
Medical history	x															
Demographics	x															
Physical exam***	x	x	x	x			x	x			x	x		x	x	x
Pregnancy test ⁵	x	x				x				x			x		x	x
Vital signs ⁶	x	x	x	x	x	x	x	x	x	x	x	x	x	x	x	x
Clinical laboratory assessments ⁷	x ⁶			x	x	x	x	x	x	x	x	x	x	x	x	x
ECG	x ⁶			x	x	x	x	x	x	x	x	x	x	x	x	x
Concomitant medication	x	x	x	x	x	x	x	x	x	x	x	x	x	x	x	x
FWS Investigator ⁸	x	x	x	x	x	x		x	x	x	x	x	x	x	x	x
FWS Subject self-assessment ⁹	x	x	x	x	x	x		x	x		x	x	x	x	x	x
Photography ¹⁰	x		x	x	x											
Psychological impact ¹¹	x			x		x		x		x		x	x	x	x	x
Treatment satisfaction ¹²				x		x		x		x		x	x	x	x	x
IMP administration	x					x				x			x			
Post treatment obs./AE assessment ¹³	x					x		x		x		x	x	x	x	x
AE and AESI assessment ¹⁵	x	x	x	x	x	x	x	x	x	x	x	x	x	x	x	x
Antibody test ¹⁴	x ⁶		x		x		x		x		x		x	x	x	x
Subject diary	D	R/D	R													

Statistical Analysis Plan (SAP)

TC = telephone contact: including assessment of concomitant medication, AEs and AESIs¹⁵ (as per AESI manual) on weeks 2 and 8 of each open-label cycle (visits 9, 11, 14, 16, 19 and 21). If an AESI is reported during a telephone contact, subjects will be asked to come to the site for further assessment including a targeted physical examination as soon as possible) * Visit numbers correspond with specific treatment and assessments. If subjects are not eligible for re-treatment at the "Evaluation for Re-treatment" visit, they will return at 4 weekly intervals thereafter, until they are eligible for treatment. The subsequent visit number for the cycle will remain the same, but will be amended with "a, b, c" etc., corresponding to the time extended (at 4 weekly intervals) in that treatment cycle. For example, the first evaluation for re-treatment is at visit 7, week 12, however for subjects who are not eligible at week 12, but at week 16, this visit will be denoted "visit 7a", while "visit 7b" will denote week 20 in the first cycle and "visit 7c" will denote week 24 etc., with each additional letter corresponding to a time point 4 weeks later in that cycle.

- ** Time differences are measured from the previous treatment administered. A time deviation of \pm 2 days is allowed for each visit, except for the week 1 visit in the first treatment cycle where a time deviation of \pm 1 day is permitted. Sites must adhere to the schedule of events and visit windows and subjects must ensure they are available for those visits. However, if for practical reasons e.g. public holidays, a visit window cannot be met, a visit can be scheduled as close as possible to that visit window. However, any deviation from the visit schedule and its associated time windows will still be documented as a protocol deviation.
- *** Full physical examination will include neurological assessment (including extraocular movements and cranial nerves) as well as assessment for muscle weakness. In addition, if the subject reports any symptoms related to Adverse Events of Special Interest (as detailed in the AESI Manual) a focused physical examination, to evaluate these symptoms will also be undertaken.
- § The ECG performed at screening is the baseline ECG. Laboratory and Anti-drug-antibody (ADA) test samples from screening are considered baseline values.
- 1 Depending on the duration of treatment effect, a maximum of 4 treatments is permitted.
- 2 Evaluation for re-treatment takes place at the earliest at 12 weeks after the first/previous treatment. Subjects who do not qualify for re-treatment at week 12 will have the option (pending eligibility) for re-treatment at 4-weekly intervals thereafter, until they are eligible for re-treatment. Once the subject is eligible for re-treatment, the end of cycle procedures will take place and the subject can receive re-treatment (i.e. the end of cycle visit and the re-treatment visit will be conducted on the same day as the Evaluation for Re-treatment visit).
- 3 The latest time for re-treatment is study week 48; if a subject is not eligible for re-treatment at study week 48, the End of Study visit will be completed.
- 4 The End of Study visit can take place in four-weekly intervals from study-week 48 until study-week 60. For subjects receiving re-treatment at week 48, the last cycle will end 12 weeks later at week 60 (=End of Study visit). End of Study visit will take place at week 48 if week 48 visit is an Evaluation for Re-treatment visit and the subject is not meeting the criteria for re-treatment. For subjects having received their last injection 8 weeks or less prior to week 48, the End of Study visit will take place 12 weeks after the last study drug treatment was given, e.g. week 52 if subject was retreated at week 40. For subjects that get prematurely discontinued from the study (at any time) the End of Study visit will take place within 1 week of discontinuation.
- 5 Only in women of child-bearing potential; blood serum test at screening and End of Study visit; otherwise urine dip stick.
- 6 Vital signs include blood pressure (diastolic /systolic) and pulse.
- 7 Laboratory Assessments: Hematology and Serum Chemistry, details in Section 11.15 of the study protocol..

Statistical Analysis Plan (SAP)

- 8 Investigator's assessment of glabellar line severity at maximum frown and at rest. Assessment will be made using the 4-point FWS [GLS-I] (0 =none, 1=mild, 2=moderate, 3=severe) and will be recorded in the CRF.
- 9 Subject's assessment of glabellar line severity at maximum frown and at rest. Assessment will be made using the 4-point FWS [GLS-S] (0 =none, 1=mild, 2=moderate, 3=severe). Subject Assessment will be performed before (ideally) and always independently of investigator assessment and will be recorded in the CRF)
- 10 Photographs of subject's glabellar lines (at maximum frown and at rest) will be taken at C1 Randomization, C1 week 2, C1 week 4 and each C1 Evaluation for Re-Treatment visit in Cycle 1 until the subject qualifies for re-treatment in order to provide evidence of effect and confirm that the subject did not qualify for re-treatment on the preceding evaluation for re-treatment visit. Although a photograph will be taken at each Evaluation for Re-treatment visit, only the photo of the visit preceding the re-treatment visit will be reviewed by the independent reviewers.
- 11 Modified Skindex-16 (GL-QoL) and FACE-Q Appraisal of Lines Between Eyebrows and Age Appraisal VAS scales will be used to measure psychological impact and concerns relating to their glabellar lines, respectively (and will be recorded in the CRF).
- 12 Treatment satisfaction will be determined using the FACE-Q Satisfaction with Outcome Scale (will be recorded in the CRF).
- 13 Subjects will be monitored for AEs during 30 minutes after administration of the IMP. No additional questioning of AESIs directly post-injection.
- 14 Anti-drug-antibody (ADA) test. If positive, serum samples will be tested for the presence of neutralizing antibodies.
- 15 AESI Questioning: active questioning by guided review of systems (ROS) as per AESI manual. If an AESI is reported, a targeted physical examination around the area of the reported AESI must follow.

AE: Adverse event; AESI: Adverse event of special interest; C: Cycle; CRF :Case report form; D:Distribution of subject diary; ECG: Electrocardiogram; FWS: Facial Wrinkle Scale; GL-QoL: Glabellar Line Quality of Life Scale; IMP: Investigational medicinal product; R:Return of subject diary; TC: telephone call; VAS: Visual analog scale

4 STUDY ENDPOINTS

4.1 Primary efficacy endpoint(s)

The primary efficacy endpoint is the proportion of subjects among BoNT/A-DP and placebo groups with a FWS score of 0 or 1 and an improvement ≥ 2 points in FWS score (at maximum frown) at the week 4 visit (of the first treatment cycle) relative to baseline (responders), based on both the investigator's and the subject's in-clinic assessments. Thus, the primary endpoint is a composite endpoint comprising investigator and subject assessments of treatment effectiveness.

4.2 Key Secondary efficacy endpoints

The key secondary efficacy endpoints of this study are:

1. The percentage of responders at maximum frown at week 12 (after the first treatment with BoNT/A-DP or placebo).
2. The percentage of responders at week 16 (after the first treatment).
3. The proportion of subjects with a ≥ 1 point reduction in FWS score at rest at week 4 in the first treatment cycle, based separately on the investigators' and the subjects' in-clinic assessments (applicable only for subjects who have a FWS score at rest ≥ 1 at baseline).
4. The percentage of responders at week 20 or later (after the first treatment).
5. The extent of change in psychological impact (emotional and social functioning and concerns relating to their glabellar lines) at week 4 after the first treatment, in the BoNT/A-DP group in comparison with placebo, relative to baseline, as assessed by the modified Skindex-16 (Glabellar Line Quality of Life Scale [GL-QoL]) and the FACE-Q (Appraisal of Lines Between Eyebrows and Age Appraisal visual analog scales (VAS)), respectively.

4.3 Additional Secondary endpoints

The additional secondary endpoints of this study are:

6. The proportion of responders among BoNT/A-DP and placebo groups with a FWS score of 0 or 1 and an improvement ≥ 2 points in FWS score (at maximum frown) during the first treatment cycle visit relative to baseline, based on both the investigator's and the subject's in-clinic assessments (composite endpoint, at weeks 1, 2 and 8).

Statistical Analysis Plan (SAP)

7. The proportion of subjects with ≥ 2 point reduction in FWS score (at maximum frown) in the BoNT/A-DP and placebo groups during the first treatment cycle visit relative to baseline, based on the independent rater's assessment of photographs (at baseline and visits 2, 4, 12, 16 and 20 weeks after treatment, within the first treatment cycle).
8. Time to onset of effect in the BoNT/A-DP and placebo groups in the first treatment cycle, as measured at weeks 1, 2 and 4 based separately on subject and investigator assessments. Onset of effect defined as at least a 1 point improvement in FWS score from baseline (at maximum frown). In addition, onset of effect will be assessed by subjects daily in the first 2 weeks after treatment, by recordings in the subject diary.
9. The extent of subject perceptions of effect of, and satisfaction with, treatment, in the BoNT/A-DP and placebo groups, during each treatment cycle, as assessed by the FACE-Q Satisfaction with Outcome Scale.
10. The proportion of subjects with a ≥ 1 point reduction in FWS score at rest in the BoNT/A-DP and placebo groups, relative to baseline, during the first treatment cycle, based on the independent rater's assessment of photos.
11. The percentage of subjects with a FWS score of 0 or 1 and an improvement of ≥ 2 points in FWS score at maximum frown (investigator and subject assessment) at four weeks after re-treatment relative to the rating at the preceding end of cycle visit.

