6.4.2.2 Additional Secondary Endpoints

6. The proportion of responders among BoNT/A-DP and placebo groups with a FWS score of 0 or 1 and an improvement ≥ 2 points in FWS score (at maximum frown) during the first treatment cycle visit relative to baseline, based on both the investigator's and the subject's in-clinic assessments (composite endpoint, at weeks 1, 2 and 8).
7. The proportion of subjects with ≥ 2 point reduction in FWS score (at maximum frown) in the BoNT/A-DP and placebo groups during the first treatment cycle visit relative to baseline, based on the independent rater's assessment of

- photographs (at baseline and visits 2, 4, 12, 16 and 20 weeks after treatment, within the first treatment cycle).
8. Time to onset of effect in the BoNT/A-DP and placebo groups in the first treatment cycle, as measured at weeks 1, 2 and 4 based separately on subject and investigator assessments. Onset of effect defined as at least a 1 point improvement in FWS score from baseline (at maximum frown). In addition, onset of effect will be assessed by subjects daily in the first 2 weeks after treatment, by recordings in the subject diary.
 9. The extent of subject perceptions of effect of, and satisfaction with, treatment, in the BoNT/A-DP and placebo groups, during each treatment cycle, as assessed by the FACE-Q Satisfaction with Outcome Scale.
 10. The proportion of subjects with a ≥ 1 point reduction in FWS score at rest in the BoNT/A-DP and placebo groups, relative to baseline, during the first treatment cycle, based on the independent rater's assessment of photos.
 11. The percentage of subjects with a FWS score of 0 or 1 and an improvement of ≥ 2 points in FWS score at maximum frown (investigator and subject assessment) at 4 weeks after re-treatment relative to the rating at the preceding end of cycle visit.

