7. SUBJECT SELECTION, WITHDRAWAL AND DISCONTINUATION

7.1 Inclusion Criteria

Subjects who meet **ALL** of the following criteria are eligible for this study:

- Aged ≥ 18 years or older at time of screening (upper limit 75 years, inclusive).
- Has moderate to severe glabellar frown lines at maximum frown (severity score of 2 or 3 on FWS) as determined by in-clinic assessments by both the investigator and the subject (where: 0= 'none', 1= 'mild', 2= 'moderate', 3= 'severe').ⁱ
- Subject has a stable medical condition with no uncontrolled systemic disease.
- Female subjects of childbearing potential must test negative for pregnancy and agree to use highly effective birth control during the course of the study. Such methods include for example: combined (estrogen and progestogen containing) hormonal contraception associated with inhibition of ovulation, progestogen-only hormonal contraception associated with inhibition of ovulation, intrauterine device, intrauterine hormone-releasing system, bilateral tubal occlusion, or vasectomized partner.ⁱⁱ
- Subjects who wear glasses must be able to adequately self-assess the severity of their glabellar lines, (according to the FWS) without glasses obstructing the forehead area.
- The moderate to severe glabellar lines have an important psychological impact on the subject as indicated by scores > 0 on either the Emotional or Functioning subscales of the modified Skindex-16 (GL-QoL).

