In general, the same statistical analyses, inclusive the additional exploratory analyses as described for the primary endpoint, will be conducted.

The analysis using the investigator’s in-clinic assessment will be conducted first with respect to the hierarchical order of key secondary endpoints, with the analysis using the subject’s in-clinic assessment second.

Statistical Analysis Plan (SAP)

All analyses (inclusive the additional exploratory analyses) on the investigator's in-clinic assessment will be conducted only for subjects who have an investigator's in-clinic assessment of a FWS score at rest > 1 at baseline. This will similarly be applied for the analyses of the subject's in-clinic assessment.

For the primary analysis (to be considered within the hierarchical testing procedure), subjects with missing investigator in-clinic assessments of FWS score at rest at baseline or week 4 visit will be assigned as being non-responders for this endpoint. This will similarly be applied for the subject's in-clinic assessment within the primary analysis.

As a consequence, the primary analysis will lead to exactly the same results as the LOCF analysis and thus the LOCF analysis will be skipped.

Analysis of key secondary endpoint 4: The percentage of responders at maximum frown (as defined above for the primary efficacy endpoint) at week 20 or later (after the first treatment).

The analysis of visit week 20 will be conducted on observed values only, i.e. missing investigator or the subject in-clinic assessments on FWS at baseline or visit week 20 will be excluded from the analysis but not assigned as being non-responders. Subjects who were re-treated before visit week 20 are considered to be non-responders.

In addition, the same analyses, inclusive the additional exploratory analyses as described for the primary endpoint, will be conducted as exploratory analyses (for subgroups also).

Analyses of other visits after first treatment but before re-treatment up to week 48 are exploratory only based on the FAS using descriptive statistics only. Subjects with re-treatment before the respective visit will be excluded from the analysis. Additional exploratory analyses, as described for the primary endpoint, will not be conducted, with the exception of the calculation of 95% CIs.

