8.6.4 Additional secondary analyses

The additional secondary efficacy endpoints will be analyzed applying the appropriate statistical method for the comparison of both treatment arms. For proportions

- of responders with a FWS score of 0 or 1 and an improvement ≥ 2 points in FWS score at maximum frown,
- of subjects with ≥ 2 point reduction in FWS at maximum frown,
- of subjects with a ≥ 1 point reduction in FWS at rest, and
- of subjects with an improvement of ≥ 2 points in FWS at maximum frown at 4 weeks after re-treatment,

the Cochran-Mantel-Haenszel test (with stratification variable site) and the Pearson χ^2 -test will be applied. In case of a total number of observations below 30, or in case of at least one cell frequency below 5, Fisher's exact test will be used instead of the χ^2 -test. Two-sided 95% CIs for response rates will be calculated, where appropriate. Additionally the cumulative proportions of effects at weeks 1, 2, and 4 will be calculated. Time to onset of effect in the first treatment cycle will be analyzed descriptively and by using the Kaplan-Meier method. Moreover, the daily assessments of the line severity when frowning will be analyzed descriptively. The FACE-Q satisfaction with outcome scale will be analyzed descriptively.

All endpoints, with exception of “responder” 4 weeks after re-treatment, will be analyzed for the first treatment cycle only. The analysis of “responder” 4 weeks after re-treatment will be conducted on observed values only, i.e. subjects with missing investigator or the subject in-clinic assessments on FWS week 4 or at the preceding end of the cycle visit will be excluded from analysis. Subjects who were treated with placebo during the first treatment cycle are excluded from the analysis of this endpoint, but not assigned as being non-responders. A two-sided McNemar test (using a significance level of 0.05) will be used to compare the response proportions between week 4 re-treatment visit and at the preceding end of the cycle visit. This endpoint will be separately analyzed for each open label extension cycle.

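### Endpoint 10 (photo-rated improvement at rest) has no baseline condition, so subjects with no lines at rest on the day 0 photograph count as non-responders in both arms and dilute the rates and their difference

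*SAP*

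**What the plan says.** Endpoint 10 appears in protocol 6.4.2.2 and SAP 4.3 as a responder proportion with a threshold of at least 1, applied to the "point reduction in FWS score at rest in the BoNT/A-DP and placebo groups, relative to baseline, during the first treatment cycle" and judged by the independent rater from photographs. SAP 8.6.4 lists it among the proportions to be tested (subjects with a ≥ 1 "point reduction in FWS at rest"), using the site-stratified Cochran-Mantel-Haenszel test and the Pearson χ² test, or Fisher's exact test when data are sparse. None of these sections limits who is counted. SAP 6.2 makes the FAS, all randomized and treated subjects, the set for efficacy.

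Key secondary endpoint 3 is the in-clinic version, with the same ≥ 1-point threshold at week 4. SAP 4.2 and protocol 6.4.2.1 make it "applicable only for subjects who have a FWS score at rest" of at least 1 at baseline.

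Entry depends on frowning only. Protocol 7.1 requires that the subject "Has moderate to severe glabellar frown lines at maximum frown (severity score of 2 or 3 on FWS", as rated in clinic by both investigator and subject. Nothing is required at rest.

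The inequality signs are not consistent. For key secondary 3, the analysis text in protocol 12.4.2 and SAP 8.6.3 has a reduction of > 1 point, and the SAP restricts to an "assessment of a FWS score at rest > 1 at baseline". For endpoint 10, the protocol synopsis has > 1 point where protocol 6.4.2.2 and SAP 4.3 have ≥ 1.

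SAP 8.6.1.1 classes all additional secondary endpoints, endpoint 10 among them, as exploratory.

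**The concern.** The scale starts at 0 (none). A subject with clear lines on frowning can have none at rest, and protocol 10.1 itself describes rest as the best appearance of the lines. Such a subject can be enrolled, cannot fall by a point at rest, and is fixed as a non-responder before treatment is given. Counting these subjects adds nothing about improvement and pulls both arms' rates towards zero.

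The plan avoids this for key secondary 3 but not for the photo-rated endpoint. At stake is how a secondary result reads. Endpoint 10 is the only at-rest endpoint scored by independent raters, and its size would depend partly on how many enrolled subjects happened to have no lines at rest.

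Endpoint 7 has a similar floor. It needs a 2-point fall at maximum frown on the photograph, while entry uses the in-clinic ratings. A subject photo-rated 1 on day 0 could not respond.

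**Working it through.** **The plan's own figure.** The documents give no expected rate, difference or power for endpoint 10. The only sample-size result (SAP section 5) is for the primary endpoint: 60% against 10%, one-sided α 0.025, 90% power, 3:1. The continuity-corrected two-proportion formula reproduces it at 42 + 14 = 56. The calculations below keep the plan's α, its 3:1 ratio and its planned arms of 525 and 175.

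**Formula.** Let f be the share of subjects whose day 0 photograph is rated 0 at rest, and let p_A and p_P be the response rates on active and placebo among those rated at least 1. Subjects rated 0 respond with probability 0, so:

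- all-subject rates: (1 − f)·p_A and (1 − f)·p_P
- difference: (1 − f)·(p_A − p_P)
- risk ratio: p_A / p_P, unchanged
- odds ratio: moves towards 1

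This takes f as equal in the two arms, which randomization gives in expectation. If p_A = p_P, the diluted rates are equal too, so type I error is not affected.

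**Assumed inputs.** f, p_A and p_P are not in the documents. I vary f up to 0.5.

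With p_A = 50% and p_P = 10% (undiluted difference 40 points):

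- f = 0.1: 45% − 9% = 36 points
- f = 0.3: 35% − 7% = 28 points
- f = 0.5: 25% − 5% = 20 points

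With p_A = 40% and p_P = 20%, power compares all 525/175 subjects at the diluted rates with the restricted subset of (1 − f) × 525 and (1 − f) × 175 at the undiluted rates (normal approximation, unstratified, no missing photographs):

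| f | All-subject rates | Difference (points) | Odds ratio | Power, all | Power, restricted |
|---|---|---|---|---|---|
| 0 | 40% vs 20% | 20 | 2.67 | 99.9% | 99.9% |
| 0.2 | 32% vs 16% | 16 | 2.47 | 99.2% | 99.6% |
| 0.4 | 24% vs 12% | 12 | 2.32 | 94.9% | 97.6% |
| 0.5 | 20% vs 10% | 10 | 2.25 | 88.9% | 94.7% |

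The restricted subset has the higher power despite being smaller. The gap between the last two columns is the avoidable loss: about 0.4, 2.7 and 5.8 points at f = 0.2, 0.4 and 0.5. For a weaker effect (30% vs 20%, f = 0.4), power is 45.3% in all subjects and 51.2% in the restricted set.

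**The case against.** The all-subject proportion is a legitimate quantity: the share of treated subjects who visibly improve at rest. Preferring the restricted version is partly a choice of estimand. The endpoint is exploratory, the avoidable power loss is small for large effects, and every magnitude above rests on assumed f and response rates. All of that stands, and it limits the point to a minor one. It does not explain why two versions of one measure, in-clinic and photographic, should have different eligibility rules.

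A reader might go further and infer that endpoint 10 is bound to come out below key secondary 3 and so look like a failed independent check. The documents do not support that:

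- The ordering follows only under the ≥ 1 definition of key secondary 3, at week 4, and if photo and in-clinic ratings agree. Read literally, the > 1 text requires a fall of at least 2 points from a baseline of 2 or 3. That is a harder response, and endpoint 10 could then be the higher of the two.
- The timing differs. Key secondary 3 is at week 4. Endpoint 10 covers the first cycle, and protocol 10.1.2 has post-treatment photographs reviewed from weeks 2 and 4 and from the visit preceding re-treatment.
- No section gives endpoint 10 the task of confirming key secondary 3, and none states why key secondary 3 is restricted. Both are inferences.

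Restricting endpoint 10 would not give the two endpoints the same denominator either, because the subsets would still be set by different raters. For endpoint 7, the floor needs a photo rating of 1 in someone whom both investigator and subject scored 2 or 3, and the documents give no frequency for that.

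**Conclusion.** The omission is real but small. As written, endpoint 10 counts any subject photo-rated 0 at rest on day 0 as a non-responder in either arm, which scales both rates and the difference by (1 − f), moves the odds ratio towards 1 and costs some power. The proportionality is exact given a common f. Its size cannot be fixed from the documents and is zero only if no such subject is enrolled. Type I error, direction of effect and risk ratio are untouched, and no confirmatory conclusion depends on this endpoint. No prediction about its rank against key secondary 3 is warranted. The inconsistent ≥ 1 and > 1 wording should be settled at the same time, since it decides what the two at-rest endpoints measure.

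**What to change.** - In SAP 4.3 and 8.6.4, analyse endpoint 10 in subjects whose day 0 photograph is rated ≥ 1 at rest by the independent rater. Report the number excluded in each arm. The all-subject rate can be kept as supportive.
- State how the day 0 rating is formed if more than one rater scores it (protocol 10.1.2 speaks of raters in the plural), and what happens if the photograph is missing.
- List the change in SAP section 9, because the protocol definition has no such limit.
- Reconcile the signs. For key secondary 3, set protocol 6.4.2.1 and SAP 4.2 (≥ 1) against protocol 12.4.2 and SAP 8.6.3 (> 1). For endpoint 10, set protocol 6.4.2.2 and SAP 4.3 (≥ 1) against the synopsis (> 1). The new restriction should not copy the > 1 wording.
- Optionally, add a supportive analysis of endpoint 7 in subjects photo-rated ≥ 2 at maximum frown on day 0.

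The cost is a few sentences and one section 9 entry. Independent rating of the baseline photographs is already planned, so no new data are needed. The subset is defined before treatment, which preserves the randomized comparison, and the subjects dropped carry no information on improvement at rest.
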